8.3.2.4. Vital Signs

Vital signs will be measured after the subject has been in the seated position for 5 minutes and will include temperature, systolic and diastolic blood pressures, pulse rate, and respiratory rate. Postural changes will be measured within 3 minutes of appropriate body position change. Body weight will also be recorded at each visit and height will be recorded at Screening.

8.3.2.5. Electrocardiogram (ECG)

Single 12-lead ECGs will be obtained at each time point during the study using an ECG machine that automatically calculates the heart rate and measures PR, QRS, QT, and QTc intervals with the subject in the supine position. The investigator or designated qualified physician at the site will evaluate the Screening ECG for any abnormalities that should exclude the subject from the

study or require acute additional evaluation or intervention. They should also evaluate the ECG printouts for all subsequent visits for any new abnormalities. Any abnormality should include a determination of clinical significance. A clinically significant ECG finding is one that requires additional medical evaluation or treatment.

8.3.2.6. Clinical Safety Laboratory Assessments

All protocol-required laboratory assessments, as defined in [Table 3](#), must be conducted in accordance with the Study Reference Manual and Protocol Time and Events Schedule ([Table 2](#)). Laboratory requisition forms must be completed and samples must be clearly labelled with the subject number, protocol number, site/center number, and visit date. Details for the preparation and shipment of samples will be provided by the laboratory and are detailed in the Study Reference Manual. Reference ranges for all safety parameters will be provided to the site by the laboratory responsible for the assessments.

Abnormal laboratory tests that are clinically significant should also be recorded as AEs on the eCRF. Clinically significant means that the confirmed abnormal test result has an impact on patient management, including additional monitoring or diagnostic tests, or changes in treatment.

The same standard applies to additional non-protocol specified laboratory assessments that are performed at the institution's local laboratory and result in a change in subject management (i.e., monitoring, diagnostic tests, or any alteration in treatment).

Refer to the Study Reference Manual for appropriate processing and handling of samples to avoid duplicate and/or additional blood draws.

Hematology, clinical chemistry, urinalysis, and other screening laboratory parameters to be tested are listed in [Table 3](#).

Table 3. Protocol-Required Screening and Safety Laboratory Assessments

Laboratory Assessments	Parameters		
Hematology	
 • Platelet count • RBC count • Hemoglobin • Hematocrit 	RBC Indices 
 • MCV • MCH 	WBC Count with Differential 
 • Neutrophils • Lymphocytes • Monocytes • Eosinophils • Basophils
Clinical Chemistry	
 • BUN • Creatinine • Glucose 	
 • Potassium • Sodium • Calcium • Chloride • Bicarbonate 	
 • AST • ALT • Alkaline phosphatase • Total and direct bilirubin • Total protein • Albumin • GGT
Every Visit through the End of Double-Blind Treatment	
 • Blood alcohol content 		
Routine Urinalysis	
 • Specific gravity • pH, glucose, protein, blood, and ketones by dipstick • Microscopic examination (if blood or protein is abnormal) 		
Screening Tests Only	
 • HBsAg • Hepatitis C antibody • TSH • Vitamin B₁₂ • Syphilis serology • Serum or urine hCG pregnancy test (as needed for women of child bearing potential, including at follow-up/early termination) • Drug screen 		

Abbreviations: ALT = alanine aminotransferase; AST = aspartate aminotransferase; BUN = blood urea nitrogen; GGT = gamma glutamyltransferase; HBsAg = hepatitis B surface antigen; hCG = human chorionic gonadotropin; MCH = mean corpuscular hemoglobin; MCV = mean corpuscular volume; RBC = red blood cell; TSH = thyroid stimulating hormone; WBC = white blood cell.

All laboratory tests with values that are considered clinically significantly abnormal during participation in the study or at the follow-up visit should be repeated until the values return to normal or baseline or until the value stabilizes. If such values do not return to normal within a period judged reasonable by the investigator, the etiology should be identified and the Medical Monitor notified.

8.3.2.7. Assessment of Suicidality

Subjects will be assessed for suicidality before and during the study using the Columbia Suicide Severity Rating Scale (C-SSRS). Subjects considered to be at significant risk will be excluded from the study. The C-SSRS is a brief measure which is designed to assess severity and change of suicidality by integrating both behavior and ideation. It assesses intensity of ideation (a potentially important marker of severity), specifically asking about frequency, duration, controllability, deterrents, and reasons for the ideation which was most severe during the respectively assessed timeframe. Suicidal behavior is also assessed by asking further questions to categorize the behaviors into actual, interrupted, or aborted attempts; as well as preparatory and non-suicidal self-injurious behavior. The C-SSRS will be completed by a rater trained and certified to administer this scale. Any change in C-SSRS score indicating the presence of suicidality should be evaluated by the investigator for clinical significance to determine continued study eligibility (Section 6.3) and appropriate clinical actions (including but not limited to a referral to a mental health professional).

Clinically meaningful suicidal ideation, suicidal behavior and completed suicide should be recorded as AEs.

8.3.2.8. Pregnancy

Details of all pregnancies in female subjects will be collected after the start of dosing and until 30 days after the last dose of investigational product. If a pregnancy is reported, then the investigator should inform the Medical Monitor within 24 hours of learning of the pregnancy.

The pregnancy must be followed up to determine outcome (including premature termination) and status of mother and child. Pregnancy complications and elective terminations for medical reasons must be reported as an AE or SAE. Spontaneous abortions must be reported as an SAE.

Any SAE occurring in association with a pregnancy brought to the investigator's attention after the subject has completed the study and considered by the investigator as possibly related to the investigational product must be promptly reported to the sponsor or the sponsor's representative.

The investigator must attempt to collect pregnancy information on any female partners of male study subjects who become pregnant while the subject is enrolled in the study. Pregnancy information must be reported to the sponsor or the sponsor's representative as described above. The partner will also be followed to determine the outcome of the pregnancy. Information on the status of the mother and child will be forwarded to the sponsor or the sponsor's representative. Generally, follow-up will be no longer than 6 to 8 weeks following the estimated delivery date. Any premature termination of the pregnancy will be reported.

8.3.3. Pharmacokinetics

Blood samples for PK analysis of RVT-101 and donepezil will be collected in a subset of patients at selected sites during the study visits indicated in Section 8.1. The actual date and time of each blood sample collection will be recorded, as well as the date and time of the previous dose of double-blind IP and/or donepezil administration. The timing of PK samples may be altered and/or PK samples may be obtained at additional time points to ensure thorough PK monitoring.

Five PK samples per subject will be taken for the purpose of assessing plasma concentrations of RVT-101 and donepezil at the following specific time points:

- At Baseline (Visit 3), the PK blood sample should be taken after cognitive testing, ECG, and vital signs measurements have been performed, and the date and time of the previous dose of donepezil will be recorded. The actual date and time of sample collection will be recorded.
- At Visit 5 (Week 6), the PK blood sample should be taken after cognitive testing, ECG, and vital signs measurements have been performed, and the time of the last dose of double-blind IP will be recorded. The actual date and time of sample collection will be recorded.
- At Visit 6 (Week 12) subjects will be instructed not to take their dose of double-blind IP in the morning but wait until in the clinic, after 1 PK sample is collected (before dosing, but after cognitive testing, ECG, and vital signs measurements have been performed). Donepezil can be taken on the regular schedule. The date and time of the previous double-blind IP and donepezil doses will be recorded along with the actual date and time of the pre-dose sample collection at Visit 6.
- At Visit 7 (Week 18), the PK blood sample should be taken after cognitive testing, ECG, and vital signs measurements have been performed, and the time of the last dose of double-blind IP will be recorded. The actual date and time of sample collection will be recorded.
- At Visit 8 (Week 24), 1 PK blood sample will be collected after cognitive testing, ECG, and vital signs measurements have been performed. The date and time of the previous donepezil and double-blind IP doses will be recorded along with the actual date and time of sample collection.
- Unscheduled PK samples may be requested by Axovant Sciences or the Medical Monitor after discussion with investigators (e.g., in cases of suspected drug reactions).

The samples will be centrifuged and the resulting plasma stored. Further details with regard to shipping, collection, and processing of samples are provided in the Study Reference Manual.

Plasma analysis will be performed under the control of Axovant Sciences, the details of which will be included in the Study Reference Manual. Concentrations of RVT-101, RVT-101 metabolites, and donepezil will be determined in plasma samples using the currently approved

bioanalytical methodology. Raw data will be archived at the bioanalytical site (detailed in the Study Reference Manual).

Once the plasma has been analyzed for RVT-101 and/or donepezil, any remaining plasma may be analyzed for other compound-related metabolites and the results reported under a separate protocol.

9. DATA MANAGEMENT

For this study, subject data will be entered into Axovant Sciences defined eCRFs, transmitted electronically to Axovant Sciences or designee, and combined with data provided from other sources in a validated data system.

Management of clinical data will be performed in accordance with applicable Axovant Sciences standards and data cleaning procedures to ensure the integrity of the data, e.g., correcting errors and inconsistencies in the data.

AEs and medical history terms will be coded using an agreed version of the Medical Dictionary for Regulatory Activities (MedDRA), using WCT coding conventions.

Concomitant medications will be coded using the World Health Organization (WHO) Anatomical Therapeutic Chemical (ATC) classification (http://www.whocc.no/filearchive/publications/1_2013guidelines.pdf).

The eCRFs (including queries and audit trails) will be retained by Axovant Sciences, and copies will be sent to the investigator to maintain as the investigator copy.

10. STATISTICAL CONSIDERATIONS AND DATA ANALYSES

10.1. Hypotheses

The primary statistical framework will be to demonstrate superiority of RVT-101 over placebo based on the ADAS-Cog-11 and ADCS-ADL change from baseline to Week 24.

The first null hypothesis is that there is no difference between RVT-101 and placebo, when added to stable donepezil, in the change from baseline in total ADAS-Cog-11 score at Week 24 in the Intent-to-Treat (ITT) Population. The first alternative hypothesis is that there is a difference between RVT-101 and placebo, when added to stable donepezil, in the change from baseline to Week 24 total ADAS-Cog-11 score in the ITT Population.

The second null hypothesis is that there is no difference between RVT-101 and placebo, when added to stable donepezil, in the change from baseline in total ADCS-ADL score at Week 24 in the ITT Population. The second alternative hypothesis is that there is a difference between RVT-101 and placebo, when added to stable donepezil, in the change from baseline to Week 24 of ADCS-ADL score in the ITT Population.

The primary comparisons of interest will be performed at the 5% level of significance. All hypothesis tests will be 2-sided, with no correction for multiple comparisons.

10.2. Sample Size Considerations

The primary comparisons of interest are to compare RVT-101 to placebo at Week 24 for change from baseline in both ADAS-Cog-11 and ADCS-ADL. A sample size of 435 subjects per treatment group will allow a difference of 1.6 points between placebo and active treatment in the change from baseline in ADAS-Cog score to be detected with 95% power and a 0.05 significance level assuming an underlying standard deviation (SD) of 6.5.

This sample size will also allow a difference of 2 points between placebo and active treatment in the change from baseline in ADCS-ADL score to be detected with 90% power and a 0.05 significance level assuming an underlying SD of 9. Sample size estimates were based on data from study AZ3110866.

Both endpoints need to achieve a significance level of 0.05 to maintain an overall 5% significance level. Hence, the multiplicity issue associated with the trial having 2 primary endpoints is addressed as efficacy will only be concluded if both endpoints are significant.

Assuming a drop-out and missing data rate of approximately 25% up to Week 24, a total of approximately 1150 subjects will be randomized in a 1:1 ratio to RVT-101 or placebo.

The impact of baseline severity and possible sub-populations of milder and more moderate subjects is an important consideration of this study. Hence, a stratified randomization will be used to enroll subjects according to their baseline MMSE score in the groupings of 10-15 points, 16-20 points, and 21-26 points.

Two subgroups using MMSE score at baseline will be examined: moderate 10-20 and mild 16-26. The thresholds for randomization presented in [Table 4](#) will be enforced.

Table 4. Baseline Mini Mental State Examination Stratification

Baseline MMSE Score	10-15	16-20	21-26
Target for recruited population	≤30%; ≥20%	≤60%; ≥40%	≤30%; ≥20%

The purpose of this ratio is to ensure that approximately 70% of the recruited population will contribute data to a data-defined subgroup analysis of either milder or more moderate subjects on ADAS-Cog-11 and/or ADCS-ADL. It is estimated that a difference from placebo of 1.6 points in ADAS-Cog-11 and 2.0 points in ADCS-ADL will be observable with approximately 80% power in a subgroup, which includes approximately 70% of subjects.

10.2.1. Sample Size Sensitivity

Based on study AZ3110866, the observed range of standard deviations for ADAS-Cog changes from baseline score was 6.13 to 6.37, and the range of observed standard deviations for ADCS-ADL changes from baseline was 8.84 to 9.36. The sample size calculation for this study used the SD of 6.5 for the ADCS-Cog endpoint and SD of 9 for the ADCS-ADL endpoint.

The robustness of the sample size calculations have been considered in order to assess the impact on the power of the study. [Table 5](#) below shows the sensitivity of the required sample size to the assumptions used in the sample size calculation.

Table 5. Sample Size Estimates with Varying Expected Treatment Differences and Standard Deviations

	Expected Difference (RVT-101 vs. Placebo)	SD	Sample Size to have at least 90% Power	Sample Size to have at least 80% Power	Power with N=435
ADAS-Cog-11	1.6	6	297	222	97.5
	1.6	6.5	348	261	95.2
	1.6	7	403	302	92.1
ADCS-ADL	1.8	8.5	469	351	87.7
	1.8	9	526	393	83.9
	1.8	9.5	586	438	79.8
	2	8.5	380	285	93.4
	2	9	426	318	90.6
	2	9.5	475	355	87.4

Abbreviations: ADAS-Cog-11 = Alzheimer's Disease Assessment Scale – Cognitive Subscale-11;

ADCS-ADL = Alzheimer's Disease Cooperative Study - activities of daily living; SD = standard deviation.

10.2.2. Sample Size Re-estimation or Adjustment

No sample size re-estimation is planned.

10.3. Data Analysis Considerations

10.3.1. Analysis Populations

The ITT Population will consist of all subjects randomized to treatment who have taken at least 1 dose of investigational product and who have at least 1 post-baseline assessment. This will be the primary population used for the efficacy analysis.

The Per-Protocol (PP) Population will consist of those members of the ITT Population who have no major protocol violations. The PP Population will not be analyzed if this population comprises more than 95% or less than 50% of the ITT Population. This population will be used for confirmatory analysis of the 2 primary efficacy variables and other cognitive and functioning endpoints. The PP Population will be identified prior to breaking the study blind.

The primary population for safety analyses will be the Safety Population, which will consist of all subjects who were randomized and took at least 1 dose of investigational product.

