6.6. Withdrawal Criteria

6.6.1. Reasons for Withdrawal

A withdrawal from the study is defined as withdrawing any time after entering the Single-Blind Run-In Phase and before completion of the Week 24 Visit (Visit 8). Subjects who permanently discontinue use of investigational product will be considered to be withdrawn from the study. Subjects may withdraw from the study at any time and for any reason. The investigator (or designee) must document the reason for withdrawal in the appropriate section of the electronic case report form (eCRF). Information related to AEs will continue to be collected as per usual

procedures on subjects who have discontinued investigational product. Withdrawn subjects will not be replaced. The reasons for subject withdrawal will be recorded and may include, but are not limited to:

- Any clinical AE, laboratory abnormality, or other medical condition or situation occurs such that continued participation in the study would not be in the best interest of the subject in the opinion of the investigator
- Pregnancy of female subject (discontinuation of treatment, but will be followed until the outcome of pregnancy is known)
- Significant protocol violation
- Subject requests to discontinue for any reason; it is important to determine whether the withdrawal of consent is primarily due to an AE, lack of efficacy, or other reason

The above reasons do not automatically lead to withdrawal from the study in all cases. The final decision will be based on consultation between the principal investigator and the study Medical Monitor, with the ultimate decision by the principal investigator or subject. Subjects may discontinue from treatment with study investigational product but may agree to continue to be followed for additional safety evaluation.

If a subject meets discontinuation criteria during treatment, an Early Termination Visit will be required (Section 6.6.2).

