7. STUDY TREATMENT

7.1. Investigational Product and Other Study Treatment

Investigational product in this study is defined as RVT-101 tablets and its matching placebo, and will be provided by Axovant Sciences. RVT-101 and placebo tablets will be indistinguishable from each other.

Investigational product for the Single-Blind Run-In Period (Weeks -3 to 0) will be supplied as single individual bottles, each bottle containing 50 tablets which is sufficient medication for 3 weeks plus 29 days overage. Investigational product for the Double-Blind Treatment Period (Weeks 0 to 24) will be supplied at Visits 3, 5, 6, and 7 as a single individual bottle containing 50 tablets, which is sufficient for 6 weeks plus 8 days overage. A new bottle of investigational product will be dispensed at each visit *except* at Visit 4, where no drug is dispensed. In the event that the Single-Blind Run-In period is extended to repeat the MMSE, no new investigational product will be dispensed. Drug accountability will be checked, and subjects will be redispensed the study medication bottles they received at Visit 2.

Subjects enrolled in this study will have been on donepezil for at least 4 months and on a stable dose of 5 or 10 mg/day for at least 2 months prior to enrollment and will continue this regimen unchanged for the duration of the study. Axovant Sciences will supply donepezil tablets in this study at the stable clinical dose for each subject. Study-dispensed donepezil will start in the Single-Blind Run-In Period. Subjects should be clearly instructed to take only study-dispensed donepezil during the duration of this study until V8, and to discontinue their clinical supply of donepezil provided by their personal physician. Subjects should be instructed to take their study-supplied donepezil exactly as they had been taking their clinically prescribed donepezil during the previous 2 months, including at the same time of day. Compliance with study-dispensed donepezil should be assessed at each visit. Confirmation of discontinuation of clinically supplied donepezil from subject and caregiver should be obtained at Visit 4 (Week 3) and re-confirmed thereafter as needed. Subjects will need to re-start their clinical supply of donepezil (clinically prescribed by the Investigator or treating physician) after V8; subjects not entering the open-label extension study RVT-101-3002 will remain at the same stable dose until V9.

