7.2. Randomization/Treatment Assignment

Subjects will be assigned to receive RVT-101 or placebo as adjunct therapy to existing stable donepezil therapy in accordance with the randomization schedule, prior to the start of the Double-Blind Treatment Period, using validated software.

Following confirmation of eligibility at Visit 3 (end of Single-Blind Run-In Period), subjects will be randomized to placebo or RVT-101 in a 1:1 ratio. Randomization will be stratified according to subjects' baseline MMSE scores, so as not to exceed the limits described in Section 10.2.

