10.4.7. Safety Analyses

The safety analyses will be based on the Safety Population.

Safety will be assessed by summarizing and analyzing AEs, laboratory analytes, vital signs, ECG parameters, physical examination findings, C-SSRS scores, and concomitant medications.

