10.4.7.1. Adverse Events

AEs will be considered treatment-emergent (TEAEs) if they start or worsen after first dose of the double-blinded treatment. If an AE begins or worsens on the first day of investigational product administration, a CRF and source data note will be provided to clarify whether it occurred prior to or after investigational product administration. TEAEs, SAEs including deaths, AEs that lead to discontinuation of investigational product, and AEs by maximum severity and relationship to investigational product will be summarized by MedDRA system organ class (SOC) and preferred term. TEAEs will also be summarized by preferred term, sorted by decreasing frequency within SOC. AEs will be summarized separately for the Single-Blind Run-In Period, the Double-Blind Treatment Period, and the Follow-up Period.

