#### 4. ANALYSIS POPULATIONS

The Intent-to-Treat (ITT) Population was defined as:

- All subjects randomized to treatment who have taken at least one dose of double-blind investigational product and who have at least one baseline (and one post baseline) primary efficacy assessment for at least one of either the ADAS-Cog-11 or the ADCS-ADL. This will be the primary population used for the efficacy analysis.

Note that the inclusion of ‘and one post baseline’ assessment was added to the original definition.

The Randomized Population was defined as all patients who are randomized.

CHMP advice suggested the following:

- “With regard to the definition of the ITT population, it is considered that the Intention-To-Treat population, as the definition already suggests, should consist of all patients randomized and the Applicant will have to justify that their definition (all randomized who took medication with one post-baseline assessment) will lead to the same conclusions on treatment effects.”

Therefore, an analysis of the **Randomized Population** will be performed for the co-primary endpoints using the multiple imputation strategy as indicated above, and the responder analyses as described for those outcomes.

A comparison of the conclusions regarding treatment effect between the Randomized Population and the ITT population will be performed. This analysis comparison will allow for justification as to whether the ITT population (as defined) leads to the same conclusions from the Randomized population.

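### The run-in adverse-event summary falls on a population limited to randomised subjects, so it omits anyone who left during run-in

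*Protocol*

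**What the plan says.** Protocol section 10.3.1 names the Safety Population as the primary population for safety, "which will consist of all subjects who were randomized and took at least 1 dose of investigational product". Section 10.4.7 then states without exception: "The safety analyses will be based on the Safety Population". Under that heading, section 10.4.7.1 says: "AEs will be summarized separately for the Single-Blind Run-In Period, the Double-Blind Treatment Period, and the Follow-up Period". The same section lists "AEs that lead to discontinuation of investigational product" among the categories to be tabulated.

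Section 7.2 fixes the time of randomisation: "Following confirmation of eligibility at Visit 3 (end of Single-Blind Run-In Period), subjects will be randomized". Section 6.6.1 covers those who leave earlier: "A withdrawal from the study is defined as withdrawing any time after entering the Single-Blind Run-In Phase". They are not screen failures, because section 6.5 keeps that term for people who never enter run-in. Section 8.3.2.1.1 records AEs from consent onward, run-in included.

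On dosing, section 7.1 says: "Investigational product in this study is defined as RVT-101 tablets and its matching placebo". It describes the run-in bottles as investigational product too. In the SAP addendum, section 4 restricts the ITT Population to randomised subjects "who have taken at least one dose of double-blind investigational product". The addendum does not restate the Safety Population.

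**The concern.** A run-in safety table should describe everyone exposed in run-in. Here, entry to the table requires randomisation, which comes after run-in and can depend on what happened there. A subject who stops in run-in because of an AE is the clearest case: the event that ought to be counted is also the reason the subject is not in the denominator.

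Suicidality shows the mechanism. Exclusion criterion 8 bars a subject who endorses C-SSRS item 4 or 5 at Baseline, and section 8.3.2.7 asks that clinically meaningful ideation be recorded as an AE. If that ideation arises in run-in, the AE is recorded and the subject is not randomised, so the AE cannot reach the run-in summary.

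What is at stake is the run-in AE incidence and the accounting of AE withdrawals before randomisation. Neither bears on the comparison of RVT-101 with placebo.

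There is also a small wording gap. Because run-in placebo counts as investigational product, a randomised subject can meet the one-dose condition before any double-blind dose. Treatment-emergent events, however, are counted from the first double-blind dose (sections 8.3.2.1.1 and 10.4.7.1).

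**Working it through.** **Step 1. Membership, from the definitions.**
- Safety Population = randomised AND at least 1 dose of investigational product (10.3.1).
- Withdrawn in run-in = entered run-in, left before randomisation at Visit 3 (6.6.1, 7.2).
- No subject meets both conditions, so the intersection is empty.
- The run-in AE summary sits under section 10.4.7 and so uses the Safety Population. AE withdrawals occurring in run-in that can appear in it = 0, whatever the true count.

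**Step 2. Are the omitted subjects exposed, with data?** Section 8.1 has subjects take the first run-in tablet during Visit 2 and dispenses study donepezil at that visit. Their AEs are recorded (8.3.2.1.1) and they count as withdrawals (6.6.1). Some exits before randomisation are to be expected, because section 8.2 stops subjects with an MMSE change of more than 3 points, or a score outside 10 to 26, from being randomised. The protocol defines no run-in, enrolled or all-treated population to hold them.

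**Step 3. The plan's own number.** Section 10.2 gives 435 per arm, about 25% dropout and about 1150 randomised.
- 435 / (1 − 0.25) = 580 per arm; 2 × 580 = 1160.
- 2 × 435 = 870, and 1 − 870/1150 = 24.3%, consistent with approximately 25%.

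The figure reproduces, and this point does not affect it. It serves below as the number randomised.

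**Step 4. Possible size.** The documents give neither the share of run-in entrants not randomised (f) nor the share who leave run-in for an AE (w). Both are assumptions here.
- Entrants = 1150 / (1 − f)
- Left out of the run-in summary = entrants − 1150
- AE withdrawals unable to appear = w × entrants

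| f (assumed) | Entrants | Left out | w = 0.5% | w = 1% | w = 2% |
|---|---|---|---|---|---|
| 5% | 1211 | 61 | 6.1 | 12.1 | 24.2 |
| 10% | 1278 | 128 | 6.4 | 12.8 | 25.6 |
| 20% | 1438 | 288 | 7.2 | 14.4 | 28.8 |
| 30% | 1643 | 493 | 8.2 | 16.4 | 32.9 |

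**Step 5. Effect on run-in AE incidence.** Let p_R be the incidence among those later randomised and p_L the incidence among those who left. Incidence in all entrants is (1 − f)·p_R + f·p_L, while the planned table reports p_R. The difference is f·(p_L − p_R). It is small when f is small or when most people leave for MMSE reasons. The documents give neither p_L nor p_R.

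**Step 6. The dose condition.** Section 8.1 has the first double-blind dose taken in the clinic at Visit 3, the randomisation visit. Few randomised subjects could have run-in doses only, so the loose wording should change the denominator very little.

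**The case against.** The strongest reply is that the final SAP of August 9, 2017 was not supplied. The addendum covers only analyses added after the EMA advice, so its silence on the Safety Population proves nothing. Section 10.3.1 says primary population, which leaves room for another, and section 10.4.9 sends further analyses to the SAP. A run-in set may already exist. This stands, and it makes the point conditional. It does not settle it, because the protocol names no other population and section 10.4.7 carries no qualifier.

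Second, a reader might infer that the data are lost. They are not. Withdrawal reasons go into the eCRF (6.6.1), a case report form is completed even for pre-randomisation failures if one was started (11.1.6), SAEs are reported within 24 hours from consent onward (8.3.2.1.3, 8.3.2.1.7), and results of all assessments go into a report appendix (10.4.9). The omission is from the summary only.

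Third, nobody takes RVT-101 in run-in, and the safety objective concerns RVT-101 as an adjunct. A reader might conclude that the tolerability of switching to study-supplied donepezil is overstated. That tolerability is not a trial objective, and the documents contain nothing to show the direction or size of any distortion.

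Fourth, section 10.4.7.1 does not say that every AE category will be repeated for run-in, so a run-in table of AE withdrawals is not expressly promised. An AE that starts in run-in and leads to discontinuation after randomisation would still be counted. The structural zero therefore applies only to withdrawals that take place during run-in.

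Finally, the addendum's ITT wording might be read as a correction of the dose condition. Section 4 of the addendum names only the post-baseline assessment as an addition, so the double-blind wording may be older. All that can be said is that it differs from the protocol's wording.

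**Conclusion.** The point holds in limited form. On the protocol's text, the run-in AE summary covers only subjects who went on to be randomised, and withdrawals during run-in because of an AE cannot appear in it. That follows from the definitions and needs no assumed rate. It does rest on the final SAP not defining a separate run-in population.

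The size is unknown. The 61 to 493 subjects left out, and the roughly 6 to 33 AE withdrawals, only illustrate assumed rates of 5% to 30% and 0.5% to 2%. An unknown share of those subjects would leave under the MMSE rule and not for safety reasons.

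A reader might go on to infer that the trial's safety conclusions are compromised. The documents do not support that. All subjects take placebo plus donepezil in run-in, and the two arms are formed only afterwards, so the double-blind comparison is not biased. The dose-wording mismatch is a nearly immaterial alignment matter.

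**What to change.** In section 10.4.7.1, state that run-in AEs, SAEs and withdrawals due to AEs will be summarised on all subjects who took at least 1 dose of single-blind run-in product, whether or not they were randomised. If the final SAP already defines such a set, cite it and bring sections 10.3.1 and 10.4.7 into line.

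As a minor alignment, define the Safety Population in section 10.3.1 as randomised subjects who took at least 1 dose of double-blind investigational product. This matches the treatment-emergent definition and the addendum's ITT dose wording. Use it for the double-blind and follow-up tables.

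The cost is one extra population flag and about two sentences. No new data are needed and no efficacy analysis changes. The run-in figures may look slightly less favourable.
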